6.5.2. Criteria for Permanent Discontinuation of Study Drug Due to an Adverse Event

The occurrence of unacceptable severity of an AE not caused by the underlying disease will be presumed to be related to study drug treatment and will require that the study drug be permanently discontinued. Unacceptable severity is defined as follows:

- Occurrence of an AE that is related to treatment with the study drug that, in the judgment of the investigator or the sponsor's medical monitor, compromised the participant's ability to continue study-specific procedures, or is considered to not be in the participant's best interest.
- Participant presents with a worsening of AD that requires treatment with a prohibited concomitant medication.
- Persistent AE requiring a delay of therapy for more than 2 weeks without resolution of the AE.

See Section 7 for discontinuation procedures.

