7. DISCONTINUATION OF STUDY TREATMENT AND PARTICIPANT DISCONTINUATION/WITHDRAWAL

7.1. Discontinuation of Study Treatment

7.1.1. Reasons for Discontinuation

Participants **must** be discontinued from study treatment for the following reasons:

- Due to lack of efficacy response during the LTS (defined as no change/improvement in either %BSA or IGA when treated continuously for 8 weeks).

- The participant becomes pregnant.

- Consent is withdrawn.

Note: Consent withdrawn means that the participant has explicitly indicated that they do not want to be followed any longer; in this case no further data, except data in public domain, may be solicited from or collected on the participant. Participants may choose to discontinue study treatment and remain in the study to be followed for progression and survival.

- Further participation would be injurious to the participant's health or well-being, in the investigator's medical judgment.

- Any adverse event of unacceptable severity as noted in Section [6.5.2](#).

- The study is terminated by the sponsor.

- The study is terminated by the local health authority, IRB, or IEC.

A participant **may** be discontinued from study treatment as follows:

- If, at 2 consecutive study visits, a participant's drug usage exceeds one 60 g tube per 4 days. The medical monitor should be consulted for instruction on handling the participant.

- If, during the course of the study, a participant is found not to have met eligibility criteria, the medical monitor, in collaboration with the investigator, will determine whether the participant should be withdrawn from study treatment.

- If a participant is noncompliant with study procedures or study drug/treatment administration in the investigator's opinion, the medical monitor should be consulted for instruction on handling the participant.

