8.7. End of Treatment and/or Early Termination

If a decision is made that the participant will permanently discontinue study drug, then the EOT visit should be conducted. If the EOT visit coincides with a regular study visit, then the EOT evaluations will supersede those of that scheduled visit, and the data should be entered in the EOT page in the eCRF. If this decision does not coincide with a regular visit, reasonable efforts should be made to have the participant return to the site to have the EOT procedures completed.

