10.4.1. Primary Analysis

The primary analysis will be based on the intent-to-treat population. The primary alternative hypothesis (superiority of ruxolitinib 1.5% BID or 0.75% BID compared with vehicle) will be tested using logistic regression. This model will include the treatment group (1.5% BID, 0.75% BID, and vehicle) and stratification factors (baseline IGA and region). The unadjusted p-values between each treatment group versus vehicle will be calculated based on Wald test, which will be compared with 0.025 using the Bonferroni procedure. Exact logistic regression ([Mehta and Patel 1995](#)) will be used for all of the comparisons if any of the dose levels have an expected cell count less than 5.

The difference in IGA-TS rates (ruxolitinib cream vs vehicle) at Week 8 will also be computed. The 95% confidence interval for the difference will be computed based on a large-sample normal approximation with continuity correction. All nonresponders in the VC treatment period, as well as all participants who discontinue study treatment at any time before the timepoint of interest, or discontinue from the study for any reason, will be defined as nonresponders for the nonresponder imputation analysis. Sensitivity analyses, including longitudinal logistic regression with repeated measurements and multiple imputation, may be performed. In addition, a tipping point analysis will be conducted to examine the potential effects of missing data. Subgroup analysis by baseline characteristic (eg, IGA, region, and age) will be performed. Details will be provided in the Statistical Analysis Plan.

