4.1.5. Handling of Missing and Incomplete Data

For response endpoints, all nonresponders, as well as all participants who are missing postbaseline values, will be defined as nonresponders for the NRI analysis.

For continuous endpoints, any participant who is missing postbaseline values may have missing data handled using MMRM under the missing-at-random assumption. MMRM model implicitly adjusts for missing data through a variance-covariance structure.

For other endpoints, missing observations will be handled as detailed in the specific sections addressing each analysis.

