7.2.2. Primary Efficacy Analyses

The primary analysis will be based on the ITT population in the VC period. The primary alternative hypothesis (superiority of ruxolitinib 1.5% BID or 0.75% BID compared with vehicle) will be tested using logistic regression. This model will include the treatment group (1.5% BID, 0.75% BID, and vehicle) and stratification factors (baseline IGA and region). The unadjusted p-values between each treatment group versus vehicle will be calculated based on Wald test, which will be compared with the procedure defined in Section 3.2. Exact logistic regression ([Mehta and Patel 1995](#)) will be used for all of the comparisons if any of the dose levels have an expected cell count less than 5.

Odds ratio and 95% CI in response rates (ruxolitinib cream vs vehicle) at Week 8 will also be computed. All nonresponders in the VC treatment period, as well as all participants who are missing postbaseline values, will be defined as nonresponders for the nonresponder imputation analysis.

The primary outcome will also be examined for PP population using the same model as the primary analysis.

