7.4.2.3. Categorical Efficacy Endpoints

For the following categorical parameters, summary statistics including sample size, frequency, and percentages will be presented by visits.

- Proportion of participants achieving an IGA of 0 or 1
- Proportion of participants with a \geq 2-point improvement in Itch NRS score
- Proportion of participants with a \geq 3-point improvement in Itch NRS score
- Proportion of participants with a \geq 4-point improvement in Itch NRS score
- Proportion of participants achieving EASI50
- Proportion of participants achieving EASI75

- Proportion of participants achieving EASI90
- Proportion of participants with a \geq 6-point improvement in the PROMIS Short Form (8a) – Sleep-Related Impairment 24-hour recall score
- Proportion of participants with a \geq 6-point improvement in the PROMIS Short Form (8b) – Sleep Disturbance 24-hour recall score
- Proportion of participants with a score of either 1 or 2 of PGIC
- Proportion of participants with a clinically meaningful improvement (\geq 4-point improvement) in DLQI/CDLQI

A logistic regression model with treatment and stratification factors as covariates will be fit at Week 8. The p-values between each ruxolitinib group versus vehicle will be calculated based on Wald test. Exact logistic regression will be used for all of the comparisons if any of the dose levels have an expected cell count less than 5. The NRI will be used to impute postbaseline missing values for binary outcomes based on IGA, EASI, Itch NRS, PROMIS Short Form – Sleep-Related Impairment (8a) scores, PROMIS Short Form – Sleep Disturbance (8b) scores.

For the following categorical endpoints, the number and percentage of participants will be summarized by treatment at each postbaseline visit.

- Proportion of participants in each category of EASI score
- Proportion of participants in each category of IGA score
- Proportion of participants in each category of PGIC score
- Proportion of participants in each category of POEM score
- Proportion of participants in each category of DLQI/CDLQI score
- Proportion of participants in each category of each EQ-5D dimension

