10.1. Changes to Protocol-Defined Analyses

- The LTS evaluable population will not be used. Efficacy and safety in LTS will be evaluated in the ITT and safety populations to keep consistency with the measurements in VC.
- Duration of AEs will not be analyzed.
- The sleep-related impairment is considered as an important endpoint. The proportion of participants with a clinically meaningful improvement (≥ 6 -point) in the PROMIS Short Form – Sleep-Related Impairment (8a-24-hour recall) score at Weeks 8 has been moved into the list of key secondary endpoints with alpha control.

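### The SAP scores Week 8 nonresponse by missing values only and drops, without declaring it, the protocol rule that stopping treatment or leaving the study is nonresponse

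*SAP*

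**What the plan says.** Protocol 10.4.1 gives the nonresponder rule for the primary endpoint, IGA-TS at Week 8. Besides observed nonresponders, it covers "all participants who discontinue study treatment at any time before the timepoint of interest" and anyone who leaves the study for whatever reason. Stopping is thus part of the outcome, and no value has to be missing.

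The SAP states the rule three times, each time in terms of missing data:
- SAP 4.1.5 covers "For response endpoints, all nonresponders, as well as all participants who are missing postbaseline values".
- SAP 7.2.2 takes observed nonresponders, "as well as all participants who are missing postbaseline values, will be defined as nonresponders for the nonresponder imputation analysis".
- SAP 7.4.2.3 says "The NRI will be used to impute postbaseline missing values for binary outcomes based on IGA, EASI, Itch NRS" and the two PROMIS sleep scores.

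None of the three mentions stopping treatment or leaving the study. SAP 10.1 declares three changes to protocol-defined analyses: the LTS evaluable population is dropped, "Duration of AEs will not be analyzed", and the sleep-related impairment endpoint becomes key secondary. The nonresponder rule is not among them.

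On visits, Protocol Table 3 puts Week 8 and end of treatment (EOT) in one column with a ±3-day window, and schedules IGA and EASI there. Protocol 7.1.2 asks for an EOT visit when treatment is permanently stopped. Protocol 8.7 adds: "If the EOT visit coincides with a regular study visit, then the EOT evaluations will supersede those of that scheduled visit".

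**The concern.** Two governing documents give different outcome definitions for the primary endpoint, so one participant can be a failure under one and a success under the other. The definitions also answer different questions. The protocol makes stopping a component of failure, while the SAP uses whatever was observed at Week 8, on or off treatment.

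The conflict is direct for IGA-TS. It reaches EASI75 less directly: Protocol 10.4.2 analyses the key secondary endpoints much as it does the primary, and the SAP makes EASI75 the primary endpoint for an EMA submission.

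The published SAP text does not say which assessments count as Week 8 data, so whether an EOT value near Week 8 is used is left to programming. That choice should be fixed before unblinding.

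**Working it through.** **1. The two rules, case by case**

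| Participant | Protocol 10.4.1 | SAP 4.1.5 / 7.2.2 |
|---|---|---|
| Stopped early, no Week 8 value | nonresponder | nonresponder |
| Stopped shortly before Week 8, value inside the window | nonresponder | scored on the value |
| On treatment, Week 8 value missing | not named | nonresponder |
| On treatment, Week 8 value present | scored on the value | scored on the value |

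The rules collide in the second row. Example: treatment stops on Day 52 and the EOT visit is on Day 55, within 3 days of Week 8. The third row is a gap in the protocol that the SAP closes.

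**2. Does any planned analysis apply the protocol rule?** Multiple imputation, last observation carried forward (LOCF) and the tipping-point analysis (SAP 7.2.4.2 to 7.2.4.4) change only missing values. The longitudinal model (7.2.4.1) contains no discontinuation rule. The per-protocol analysis excludes participants with prohibited medication or compliance below 60% (SAP 6.3), but does not count them as failures. So none does.

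**3. The plan's power figure.** Inputs from Protocol 10.1: 600 randomized 2:2:1 (240, 240, 120), rates 45%, 30% and 10%, Fisher exact test, two-sided alpha 0.025. Exact enumeration gives 98.9% for 30% vs 10% and above 99.9% for 45% vs 10%. The stated figure of over 95% reproduces.

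**4. Illustrative size.** Points added to an arm = d × f × r.
- d, share stopping before Week 8. From the Phase 2 study (Protocol 2.2.2.4.1), 46/307 = 15.0%. Without the 13 lost to follow-up and 20 withdrawals, (46 − 13 − 20)/307 = 13/307 = 4.2%.
- f, share of stoppers with an in-window value. The documents give none. Assumption: stopping is uniform over 56 days and the EOT visit falls within 3 days of stopping. Only the last 3 + 3 = 6 days then qualify, and 6/56 is about 11%. The true range is 0 to 100%.
- r, response among them. Assumption: the arm's design rate.

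| Arm | d = 4.2% | d = 15.0% |
|---|---|---|
| Vehicle, r = 10% | 4.23 × 0.11 × 0.10 = 0.05 | 14.98 × 0.11 × 0.10 = 0.16 |
| 0.75%, r = 30% | 4.23 × 0.11 × 0.30 = 0.14 | 14.98 × 0.11 × 0.30 = 0.49 |
| 1.5%, r = 45% | 4.23 × 0.11 × 0.45 = 0.21 | 14.98 × 0.11 × 0.45 = 0.74 |

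In participants, the upper column is about 120 × 0.0016 = 0.2, 240 × 0.0049 = 1.2 and 240 × 0.0074 = 1.8. At f = 0 nothing changes. At f = 100% the additions would be 0.42 to 1.50, 1.27 to 4.50 and 1.91 to 6.74 points.

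**5. Direction.** At the design rates, the 0.75% difference rises from 20.0 by 0.14 − 0.05 = 0.09 to 0.49 − 0.16 = 0.33 points. The 1.5% difference rises from 35.0 by 0.16 to 0.58. If only vehicle stoppers had usable values, both differences would fall by 0.05 to 0.16. A deliberately extreme case for 0.75% takes d = 15%, f = 100%, and 0% response on active against 30% on vehicle among stoppers. It gives 30.0% vs 10 + 15 × 0.30 = 14.5%, a difference of 15.5 points and power of 85.2%. This shows only that the sign is not assured; it is not an expected result.

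**The case against.** The strongest reply is delegation. Protocol 10.4 calls itself a summary and leaves missing-data procedures to the SAP, and 10.4.1 defers details there too. But the protocol states the discontinuation rule itself, and that rule covers participants whose data are not missing. Replacing it is a change to a protocol-defined analysis, which SAP 10.1 exists to record.

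The second reply is that the route is narrow, and this largely stands. An EOT visit supersedes only a coinciding visit, and Week 8 is only ±3 days wide. The protocol schedules no further vehicle-controlled visits after EOT. Having a separate LOCF analysis implies that earlier values are not Week 8 data. A reader might point to Protocol 7.1.1, "Participants may choose to discontinue study treatment and remain in the study", but that sentence sits in a note on withdrawn consent and goes on to speak of progression and survival; it schedules no Week 8 efficacy visit. Follow-up could supply IGA but not EASI (Table 4), and only if relabelled as Week 8, which is not the natural reading of SAP 7.1. The diary-based itch and sleep endpoints are largely protected, because diaries end when treatment stops.

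Three stronger readings are tempting, and the documents do not support them.
- A reader might infer that someone taken off drug under Protocol 6.5.2 ("Participant presents with a worsening of AD that requires treatment with a prohibited concomitant medication") could count as a success. The EOT assessment would be made near the worsening, and success needs IGA 0 or 1 with a two-grade improvement, so this is implausible.
- A reader might infer that the SAP rule can only raise response rates. The protocol does not name the on-treatment participant who misses Week 8, whom the SAP makes a nonresponder, so this cannot be asserted.
- A reader might assume that a large share of stoppers, say half, is affected. Nothing in the documents supports that, and the visit structure points to a minority.

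**Conclusion.** The SAP is wrong as written on this point. Followed literally, it can score as a responder on the primary endpoint a participant whom the protocol scores as a nonresponder, and the change is neither declared nor covered by a sensitivity analysis.

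The expected effect is small: under the stated assumptions, fewer than 2 participants in any arm and under 1 percentage point. That size rests on Phase 2 stopping rates, an unsourced 11% share of in-window values and response at the design rates; the documents supply neither of the last two. Most early stoppers would be nonresponders under both rules.

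This is a conflict of definition, not a power error. Sample size, alpha and the stated power are unaffected at the design rates.

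**What to change.** Put one merged rule in SAP 4.1.5, 7.2.2 and 7.4.2.3. A participant is a nonresponder if study treatment was permanently discontinued or the study was left before Week 8 (the protocol clause), or if the Week 8 value is missing (the SAP clause, which also covers on-treatment participants who miss the visit).

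State the Week 8 window, and two consequences:
- EOT or follow-up assessments outside it are not Week 8 data.
- An in-window EOT visit of a participant who completed the vehicle-controlled period is Week 8 data, even if that participant does not enter the extension.

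Keep the SAP's observed-value rule as a sensitivity analysis. If the change was intended, declare and justify it in SAP 10.1 and report the protocol rule as the sensitivity analysis.

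The cost is a few sentences and one programming flag, since SAP 6.2 already summarises discontinuation and withdrawal in the vehicle-controlled period. The downside is that response rates may be slightly lower.

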7.2.3. Subgroup Analyses for Primary Endpoints

Subgroups will be formed based on the following participant characteristics and baseline variables for those participants whose data are available:

- Baseline IGA score (2, 3)
- Baseline EASI score ($\leq 7, >7$)
- Region (North America, Europe)
- Categorical age
- Sex
- Race

7.2.4. Sensitivity and Supportive Analyses for Primary Endpoints

7.2.4.1. Longitudinal Logistic Regression With Repeated Measures

To adjust for the dependence underlying the hierarchical multilevel data structure (visit, participant, and site), a longitudinal logistic regression with repeated measures will be applied.

The 3 level structures in the model are:

- Level 1: visit;
- Level 2: participant; and
- Level 3: site,

where visits are nested within participants, which are further nested within sites.

The binary response (IGA-TS or EASI75) of each participant at Week 2, Week 4, and Week 8 will be included as the dependent variable. Treatment (1.5% BID, 0.75% BID, and vehicle BID), the randomization stratification factors (baseline IGA and region), visit, and treatment by visit interaction will be included as fixed effects. Site level intercept and participant nested in site level intercept will be included as random effects. The within-participant and within-site errors will be modeled by an unstructured variance-covariance matrix. The Kenward-Roger approximation will be used to estimate denominator degrees of freedom for this model.

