10. STATISTICS

10.1. Sample Size Determination

Approximately 600 participants will be randomized 2:2:1 to ruxolitinib 0.75% BID, 1.5% BID, or vehicle and stratified by baseline IGA (2, 3) and region (North America or other). The sample size calculation is based on the Fisher exact test for the statistical comparison on the primary efficacy endpoint. The Fisher exact test is used to provide a conservative evaluation of statistical power, and it is accurate when there is a small expected number of responders in the vehicle group. Based on the results from a Phase 2, randomized, dose-ranging study (INCB 18424-206), the IGA-TS at Week 8 is assumed to be 45% and 30% for active arms (1.5% BID and 0.75% BID, respectively) versus 10% for placebo. Using a 2-sided alpha of 0.025, the sample size will have > 95% power to detect a difference between each of the 2 active treatment groups versus vehicle. In addition to provide adequate power for efficacy variables, the sample size is determined to provide an adequate database for safety evaluation.

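### The longitudinal logistic sensitivity model (SAP 7.2.4.1) specifies participant dependence twice and an undefined within-site matrix, with no fallback and no named result

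*SAP*

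**What the plan says.** SAP 7.2.4.1 is the first sensitivity analysis listed for the primary endpoint. It describes three nested levels (visit, participant, site), and "The binary response (IGA-TS or EASI75) of each participant at Week 2, Week 4, and Week 8 will be included as the dependent variable". Fixed effects are treatment, the two stratification factors, visit, and treatment by visit. Three statements then set the dependence structure and the inference:

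- Random effects: one intercept for each site and one for each participant, the second nested in the first.
- Error covariance: "The within-participant and within-site errors will be modeled by an unstructured variance-covariance matrix".
- Inference: denominator degrees of freedom by the Kenward-Roger method.

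The section names no estimation method, no simpler structure to use if the model fails to converge, no contrast to report, and no handling of missing visits.

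The primary analysis in SAP 7.2.2 is a Week 8 logistic regression on treatment, baseline IGA and region, with no random effects. Missing data are handled by single imputation: "all participants who are missing postbaseline values, will be defined as nonresponders for the nonresponder imputation analysis". On the effect measure it says "Odds ratio and 95% CI in response rates (ruxolitinib cream vs vehicle) at Week 8 will also be computed".

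Protocol 10.4.1 lists the longitudinal analysis as optional; the SAP makes it definite.

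**The concern.** A participant intercept makes a participant's three visits correlated. An unstructured 3x3 within-participant error matrix does so too, and in full generality. Asking for both leaves the software to divide one quantity between two places. The within-site matrix adds a third layer that the text never defines.

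If the fit fails, someone has to choose a simplification, and the SAP gives no order. One choice gives an odds ratio with no participant effect, like the primary. The other gives a participant-specific odds ratio, which is usually further from 1 even when no data are missing. Set beside the primary odds ratio, a larger value could be taken as evidence of robustness when it reflects only a change of scale.

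**Working it through.** **Inputs from the documents.** Three binary visits (SAP 7.2.4.1). "Approximately 600 participants will be randomized 2:2:1 to ruxolitinib 0.75% BID, 1.5% BID, or vehicle" (Protocol 10.1), which gives 240/240/120. Week 8 IGA-TS rates of 45%, 30% and 10% (Protocol 10.1, SAP 3.3). The documents give no figure for the longitudinal model itself. The figure they do give, power above 95% per dose at two-sided alpha 0.025, is reproduced: the exact Fisher calculation at 240 versus 120 gives 98.9% for 30% v 10% and over 99.99% for 45% v 10%.

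**Step 1: redundancy.** An unstructured 3x3 matrix has 3 × 4 / 2 = 6 distinct entries. A participant intercept adds one common constant to all 6 on the linear-predictor scale.
- For one set of visit-specific response rates, the 7 parameters act on 6 entries: rank 6, so one is exactly redundant.
- Across three arms with different rates, the error variance scales with 1/[p(1 − p)] and so differs by arm. Stacking the arms gives rank 7. That mean-variance relation is the only source of separation. This check assumed earlier-visit rates of 20/35%, 13/23% and 4/7% at Weeks 2/4 for 1.5%, 0.75% and vehicle.

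**Step 2: the within-site matrix.** Read literally, a site with m participants has 3m observations, and an unstructured matrix has 3m(3m + 1)/2 terms.
- m = 6: 18 × 19 / 2 = 171.
- m = 10: 30 × 31 / 2 = 465.

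The values of m are assumed. Sites of different size have matrices of different dimension, so there is no common matrix to estimate.

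**Step 3: does it fit?** Eleven simulated trials of 600 with complete data, fitted by restricted pseudo-likelihood. Assumed: 60 sites of 10, the earlier-visit rates above, and two correlation patterns. The within-site matrix was left out because it is undefined. Odds ratios are for Week 8, 1.5% v vehicle, relative to the primary logistic odds ratio in the same trial.

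| Model | Converged | Odds ratio against primary |
|---|---|---|
| Site intercept + unstructured 3x3, no participant intercept | 11/11 | about −3% to +6% |
| Site and participant intercepts only | 11/11 | +8% to +37% |
| Both, as written | 2/11, 1/11 and 7/11 from three sets of starting values | same as the first row when converged |

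The 7/11 came from starting at the first row's solution. In every converged fit as written the participant variance was below 0.01. In one trial the odds ratio was 7.92 against 7.87 for the primary. Examples for random intercepts only: 9.81 against 8.31, and 14.84 against 10.81. For 0.75% v vehicle the random-intercept odds ratio ran from 3.13/3.22 (−3%) to 7.00/5.94 (+18%), so it is usually but not always larger.

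**Step 4: the scale gap.** With no participant effect the planning rates give
- (0.45/0.55)/(0.10/0.90) = 7.36
- (0.30/0.70)/(0.10/0.90) = 3.86

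With a normal participant intercept of variance σ², the marginal rate is p = ∫ expit(a + σu)φ(u)du. Solve for a in each arm; the conditional odds ratio is exp(a₁ − a₀). The latent ICC is σ²/(σ² + π²/3).

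| Latent ICC (assumed) | σ² | 45% v 10% | 30% v 10% |
|---|---|---|---|
| 0 | 0 | 7.4 | 3.9 |
| 0.3 | 1.41 | 11.5 | 5.1 |
| 0.5 | 3.29 | 18.6 | 6.9 |
| 0.7 | 7.68 | 45 | 12.2 |

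These are the theoretical conditional values. The pseudo-likelihood fits in Step 3 showed a much smaller gap.

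**Step 5: does the test statistic move?** Forty complete-data trials per setting at the same ICCs, fitted by maximum likelihood with no site effect or covariates. The median ratio of the Week 8 Wald z, random-intercept to simple logistic, was 1.01 to 1.03. At ICC 0.7, 1.5% v vehicle, the median odds ratio rose from 7.8 to 54 while the median z was 6.13 against 6.22.

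**The case against.** **Can three binary visits support an unstructured matrix?** A reader might infer that they cannot. They can: without the participant intercept it fitted in 11 of 11 trials. The fault lies in the combination.

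**Is the model certain to fail?** A reader might also infer this. It sometimes converges, and then the participant variance is about zero and the odds ratio is close to the primary one. If unstructured is taken to describe the random-effect covariance, each level has a single variance and the model fits. The SAP refers to errors, so this is not the plain reading, and it leads to the participant-specific odds ratio.

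**Would the result look falsely significant?** Step 5 does not support that. The standard error grows with the estimate, and the z statistic barely moves. What stands is narrower: the sizes of the two odds ratios should not be compared. SAP 7.2.4.1 does not itself say that an odds ratio will be reported.

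**Would the replacement model be chosen after unblinding?** The documents do not say so. SAP 9 puts sponsor unblinding after the primary database lock, and nothing prevents a trial run on dummy assignments and an amendment before then. The gap is only that no order of simplification is written down.

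**Does it matter?** Multiple imputation, last observation carried forward and a tipping-point analysis (SAP 7.2.4.2 to 7.2.4.4), and the per-protocol run in 7.2.2, also probe the primary result. Among the IGA-TS tables in SAP Appendix A only the tipping-point analysis has its own sensitivity table. This limits the weight of the point but does not make the specification workable.

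**Conclusion.** The specification is wrong as written, and the consequence is small. The participant intercept is redundant with the unstructured within-participant matrix except through variance differences between arms, and the within-site unstructured matrix has no definition. Convergence is unreliable and, when reached, degenerate in the participant variance. The SAP states neither a fallback nor a result to report, and the two obvious simplifications answer on different scales.

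The rank result and the existence of a conditional-marginal gap do not depend on any fitter. The convergence counts and the 8% to 37% excess do: they come from 11 simulated trials, a purpose-written pseudo-likelihood routine rather than SAS, and assumed site numbers, earlier-visit rates and correlations. The size of the theoretical gap depends on the assumed ICC.

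The primary test, the alpha-controlled hypotheses in SAP 3.2 and the sample size are unaffected.

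**What to change.** Amend SAP 7.2.4.1 before unblinding:

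1. Delete the participant random intercept and the within-site unstructured matrix. Keep the unstructured 3x3 within-participant matrix over Weeks 2, 4 and 8, with the site intercept if site adjustment is still wanted.
2. Name the estimation method and a fallback order, for example unstructured and then exchangeable.
3. Name the Week 8 contrast of each dose with vehicle as the reported result, on a population-averaged scale. If the site intercept stays, average over the site effect.
4. State how missing visits are handled, and keep the Kenward-Roger step only if the chosen estimation method supports it.

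A marginal model of GEE type is one acceptable form, but it is a trade-off. Unweighted GEE needs stronger missing-data assumptions than missing at random, and it drops the site adjustment unless that is added separately. If it is used, say so and point to the multiple imputation in 7.2.4.2 as the analysis that covers missing at random.

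The cost is SAP wording and simpler code. Data collection, design and sample size do not change.
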